## 6.10. Concomitant Therapy

Concomitant medications will be coded and descriptively summarized by treatment group in terms of frequencies and percentages using the mITT population.

Medications taken during JAİM that started before the last date of the treatment period and are ongoing or ended during the treatment period will be classified as "concomitant" medication.

The baseline for concomitant medications is defined as the medication and dose taken on the day prior to the date of the first dose of study drug administration (baricitinib).

For Zoster and tuberculosis (TB) vaccine, since only start date is reported, if start date is missing, these medications will be considered to be prior therapy.

Patients may continue to receive the background standard therapies for SLE they were receiving at completion of the originating study. Changes in dose of background standard therapies for SLE, such as an increase in dose of antimalarials or immunosuppressants, are permitted during the study. In addition, changes in concomitant medication, such as an increase in corticosteroids to manage any increase in disease activity or corticosteroid tapering, are permitted during the study in accordance with long term management of disease activity and at the investigator's discretion. Any required corticosteroid bursts should be aligned with clinical practice.

Prohibited concomitant medications are defined as

- initiation of new antimalarials or immunosuppressants
- recurrent intravenous injection of any corticosteroids, or
- having any other biologics or protocol-prohibited concomitant medications, defined from the ATC codes of L01XC, L01XX, L04AB, L04AC, V98, or J06B (excluding J06BB).

Prohibited medications during the treatment period will be reviewed by the study team to assess clinical significance of change in medication. The final determination of clinical meaningfulness will be documented and will be incorporated into the analysis datasets.

Concomitant medication use during Study JAIM will be summarized by treatment, organized according to ATC code level 1 and preferred name, sorted by frequency in the placebo to baricitinib 4-mg group. The summaries of concomitant medications will be provided overall and separately for concomitant medications used to treat SLE and for statin concomitant medications. Note that a patient will only be counted once, regardless of how many times medication included under the same preferred name was taken.

A by-patient listing of all concomitant medications will be provided for the mITT patients.

For corticosteroids, all doses of steroids will be converted to an equivalent dose of prednisone (see Section 6.10.1). Using the prednisone-equivalent dose, a daily dose of corticosteroid will be derived for each study day from baseline to the treatment discontinuation day for patients who discontinue treatment early or to the day before for treatment completers.

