7.7. Concomitant Therapy

Patients may continue to receive the background standard therapies for SLE they were receiving at completion of the originating study. Changes in dose of background standard therapies for SLE, such as an increase in dose of antimalarials or immunosuppressants, are permitted during the study. Initiation of new antimalarials or immunosuppressants are prohibited during the study.

In addition, changes in concomitant medication, such as an increase in corticosteroids to manage any increase in disease activity or corticosteroid tapering, are permitted during the study in accordance with long term management of disease activity and at the investigator's discretion. Any required corticosteroid bursts should be aligned with clinical practice.

Prohibited concomitant treatments include those outlined in the exclusion criteria of the originating trials.

- Scheduled parenteral corticosteroids, biologic treatments for immunologic disease, cyclophosphamide, belimumab, anifrolumab (or any other anti-IFN therapy), rituximab, any other B cell depleting therapies, intravenous immunoglobulin or any other JAK inhibitors.

Any changes to the patient's medication must be discussed with the investigator. Patients should be instructed to consult the investigator or other appropriate study personnel at the site before taking any new medications or supplements.

Additional medications are to be avoided during the study unless required to treat an AE or for the treatment of an ongoing medical problem.

Any additional medication, whether prescription or over-the-counter, used at baseline and/or during the course of the study must be documented in the eCRF with start and stop dates.

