#### **6.4.2.2. Non-responder Imputation (NRI)**

The NRI method may be used when the estimand of interest uses the composite strategy (EMA 2020) for handling intercurrent events. In this strategy, patients with any intercurrent event that leads to the permanent discontinuation of assigned study treatment or to prohibited medication use are defined to have failed treatment for that particular visit interval but not for the subsequent visit intervals (as defined in Section 6.4.2). Therefore, using a composite estimand approach, no data would be missing and the function of the NRI is to estimate the estimand.

All patients who discontinue the study or permanently discontinue study treatment at any time for any reason or patients who have a prohibited medication in a particular visit interval will be defined as non-responders for that visit interval and excluded from the subsequent visit intervals. Enrolled patients without at least one postbaseline observation will be defined as non-responders for the first visit interval (Visit 6) and excluded from evaluation in subsequent visit intervals.

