### **6.10.1. Corticosteroid Dosing Conversion**

To allow for assessments of changes in doses of various corticosteroids, all corticosteroid doses will be standardized to an equivalent prednisone dose. [Appendix 1](#) provides a complete summary of conversion factors for each corticosteroid medication identified during the study, instructions for selecting corticosteroids, and the manual review process. An intramuscular (IM) injection is considered a single dose on the date IM injection is administered. This dose of corticosteroid will be referred to as “prednisone (or equivalent)” throughout this document.

Baseline prednisone (or equivalent) dose will be the total daily dose of all corticosteroids being taken by a patient on the day prior to the date of the first dose of study drug administration (baricitinib). This baseline dose will be used for baseline summaries and for comparisons to later visits. A daily dose of prednisone (or equivalent) will be calculated for each day between baseline and study discontinuation. The corticosteroid dose for a postbaseline visit will be the daily dose of prednisone (or equivalent) at each visit date minus 1.

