### Corticosteroids

The following ATC codes will be used to select all possible systemic corticosteroids:

- H02 Corticosteroids for systemic use (except H02AA Mineralocorticoids), specifically
  - H02AB Glucocorticoids
  - H02BX Corticosteroids for systemic use, combinations
  - H02CA Anticorticosteroids,

and additionally

- M01BA Anti-inflammatory/antirheumatic agents in combination with corticosteroids

All unique preferred names in the database falling under the above ATC codes will be reviewed by the Lilly Medical Group in order to determine which ones should be included.

For each patient who has recurrent, intravenous injection of any corticosteroids with a start date or stop date during the treatment period (ie, from the date of randomization to the day of completion/early termination), the medications for this patient will be reviewed and the patient will be classified as having “prohibited” or “not prohibited” use during the treatment period.

Note: determination of prohibited use is based on a case-by-case assessment of recurrent intravenous corticosteroid use, considering if dose and/or duration of use are clinically relevant.

All corticosteroid doses need to be converted to prednisone equivalent doses. If additional conversion factors are required, these will be added to the table below in a SAP revision prior to database lock.

The following table should be used for converting nonprednisone medications to prednisone equivalent:

Multiply the dose of the corticosteroid taken by the patient (in milligrams) in Column 1 by the conversion factor in Column 2 to get the equivalent dose of prednisone (in milligrams).

*Example: Patient is taking 16 mg of methylprednisolone po daily. To convert to prednisone:  $16 \text{ mg methylprednisolone} \times 1.25 = 20 \text{ mg prednisone}$ . 16 mg of methylprednisolone po daily is equivalent to 20 mg of prednisone po daily.*

Column 1	Column 2
Corticosteroid Preferred Name	Conversion factor for converting to an equivalent prednisone dose
Prednisone	1
Prednisone acetate	1
Prednisolone	1
Prednisolone acetate	1
Prednisolone sodium phosphate	1
Methylprednisolone	1.25
Methylprednisolone acetate	1.25
Methylprednisolone sodium succinate	1.25
Triamcinolone	1.25
Triamcinolone acetonide	1.25
Triamcinolone hexacetonide	1.25
Cortisone	0.2
Cortisone acetate	0.2
Hydrocortisone	0.25
Hydrocortisone acetate	0.25
Hydrocortisone sodium succinate	0.25
Betamethasone	6.25
Betamethasone acetate	6.25

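### The SAP's prohibited-corticosteroid flag covers only recurrent intravenous use, while the protocol prohibits scheduled parenteral use, so scheduled intramuscular use does not itself trigger the intercurrent-event rules

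*SAP*

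**What the plan says.** Protocol 7.7 opens its list of prohibited treatments with "Scheduled parenteral corticosteroids, biologic treatments for immunologic disease, cyclophosphamide". The corticosteroid entry is limited by schedule, not by route. The same section permits corticosteroid increases, tapering and bursts.

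SAP 6.10 defines prohibited medication in three parts: new antimalarials or immunosuppressants; "recurrent intravenous injection of any corticosteroids"; and "having any other biologics or protocol-prohibited concomitant medications, defined from the ATC codes of L01XC, L01XX, L04AB, L04AC, V98, or J06B" (excluding J06BB).

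The case-by-case corticosteroid review in SAP Appendix 1 has this entry condition: "For each patient who has recurrent, intravenous injection of any corticosteroids with a start date or stop date during the treatment period".

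Prohibited-medication status then drives three rules:

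- **NRI (SAP 6.4.2.2):** "patients who have a prohibited medication in a particular visit interval will be defined as non-responders for that visit interval", and they are left out of later intervals.
- **MMRM (SAP 6.4.2.3):** data after the first date of prohibited use are dropped.
- **mLOCF (SAP 6.4.2.4):** the last value at or before the use is carried forward within that interval.

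The SAP anticipates intramuscular records. Section 6.10.1 has a dose rule for them: "An intramuscular (IM) injection is considered a single dose on the date IM injection is administered".

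**The concern.** Intramuscular injection is a parenteral route. If the protocol prohibits scheduled parenteral corticosteroids and the analysis flag recognises only the intravenous route, a patient can be on treatment that the protocol prohibits and still be analysed as if no intercurrent event had occurred.

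This matters because SAP 6.4.2.2 presents NRI as estimating a composite estimand in which prohibited medication counts as treatment failure. The protocol's description of BILAG B (section 9.1.1.3) names intramuscular corticosteroid injections among the treatments for moderate activity, so such use bears on the disease measures being analysed. At stake are the long-term SRI, BICLA and LLDAS response rates and the within-arm mean changes.

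**Working it through.** There is no plan figure to reproduce. The check sets the texts side by side and then works out what the gap does to an NRI rate.

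**1. Does the catch-all close the gap?** Appendix 1 selects systemic corticosteroids from H02AB, H02BX, H02CA and M01BA. The prohibited list in SAP 6.10 is L01XC, L01XX, L04AB, L04AC, V98 and J06B. None of the four corticosteroid codes falls under any listed code (0 of 4). The third part of the definition does refer to protocol-prohibited medications, but it defines them by this list, so it cannot pick up a corticosteroid.

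**2. Does a review step close it?** The preferred-name review in Appendix 1 decides which products count as corticosteroids, not whether their use was prohibited. The case review starts only for recurrent intravenous use. The study-team review in SAP 6.10 covers medications already defined as prohibited. None of these reaches scheduled intramuscular use.

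**3. Do the dose endpoints act as a backstop?** Only weakly. An intramuscular dose counts on its own date, and SAP 6.10.1 reads the visit dose at visit date minus 1. If injections are given every d days, unrelated to visits, the chance that one falls on that day is 1/d. For assumed intervals:

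- 14 days: 1/14 = 7.1%
- 28 days: 1/28 = 3.6%
- 84 days: 1/84 = 1.2%

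An injection on that day can fail the LLDAS dose criterion (at most 7.5 mg/day), but most would not be seen. The single-day rule is a separate derivation choice, and it matters here only because it does not repair the flag.

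**4. Effect on an NRI rate.** Let s be the share of the denominator with unflagged use who stay on drug, r1 their response rate and r0 the rate in everyone else. Assume that the case review would have confirmed all of the use as prohibited.

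- *Interval of first use.* As written, the rate is (1−s)r0 + s·r1. With the flag it is (1−s)r0. The overstatement is s·r1.
- *Later intervals.* As written, the rate is again (1−s)r0 + s·r1. With the flag these patients leave the denominator, so it is r0. The difference is s(r1−r0).

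For the interval of first use, the table takes s as 1%, 3% or 5% (assumed) and r1 as the Phase 2 SRI-4 rates in protocol 3.1:

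| s | r1 = 51.4% (2-mg) | r1 = 64.4% (4-mg) |
|---|---|---|
| 1% | 0.5 points | 0.6 points |
| 3% | 1.5 points | 1.9 points |
| 5% | 2.6 points | 3.2 points |

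For later intervals with s = 5%: if r1 = r0, the difference is 0. If r1 is an assumed 20 points below r0, it is 0.05 × (−20) = −1.0 point, so the rate as written is lower than the flagged rate.

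**5. Effect on the MMRM.** Flagging would delete these patients' later data under a missing-at-random assumption. If the steroid has improved their scores, keeping the data flatters the arm. If they are doing worse than the rest, keeping the data makes the mean change look worse. The documents do not settle which.

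**The case against.** A reader might infer that scheduled intramuscular use is never treated as failure and that efficacy is therefore biased upward throughout. The documents do not support that, for four reasons.

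- **Protocol 8.1.2.** Study drug must be stopped before a patient starts another SLE agent that breaks the 7.7 rules. Permanent discontinuation is non-response under NRI and a carry-forward trigger under mLOCF. This stands, and it confines the gap to patients who stay on study drug. It does not close the gap: SAP 6.4.2.2 lists prohibited medication separately from discontinuation, and if 8.1.2 were enough, the intravenous, biologic and immunosuppressant flags would be unnecessary too. It is also open to interpretation whether an injection in a patient already taking a corticosteroid counts as another agent.
- **Exclusion from later intervals.** The key time point is Week 156. Use first occurring by Week 108 would, if flagged, remove the patient from the Week 156 denominator and not turn a responder into a failure. Share times response rate is therefore not a general estimate.
- **Inputs.** No rate of scheduled intramuscular use is given, an average response rate may not suit patients who need repeated injections, and the case review might class some use as not prohibited. These points stand.
- **Visibility and importance.** Efficacy is not a primary outcome (SAP 6.11.2). Observed-case summaries accompany NRI. Concomitant medications are listed by patient, and important deviations are listed and summarised. This limits the consequence, but a listing does not change how a patient is counted.

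**Conclusion.** The mismatch is real and nothing elsewhere in the SAP repairs it. Scheduled parenteral corticosteroid by a non-intravenous route is not itself a prohibited-medication trigger. A patient who receives it and stays on study drug can be an NRI responder in that interval and keeps later data in the MMRM and mLOCF analyses, contrary to the SAP's stated intercurrent-event handling.

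The NRI rate can be overstated in the interval of first use. The 0.5 to 3.2 points shown apply only there, and only under the assumed 1% to 5% share, Phase 2 response rates and confirmation of every case at review. For later intervals and the MMRM the direction is undetermined, so a general claim of upward bias is not supported. With no rate of use in the documents, no overall size can be given.

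SAP 6.1 plans no inferential comparison of treatment groups unless otherwise stated, so the effect is on descriptive rates and within-arm changes. Confidence is high for the text mismatch and low for how much it matters numerically.

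**What to change.** Before database lock, reconcile protocol 7.7 with SAP 6.10 and Appendix 1 so that the analysis flag matches the category the protocol prohibits. Which corticosteroid rule is right is a clinical matter for the sponsor, and this review does not choose one. The reconciliation should also settle whether scheduled (protocol) and recurrent (SAP) are meant to be the same thing.

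Then widen the entry condition for the Appendix 1 case review to scheduled or recurrent corticosteroid use by any recorded parenteral route. Leave the decision on each patient to that review, and document it as SAP 6.10 already requires.

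The cost is a wording change in two places in the SAP and a slightly longer medication review list. The Appendix 1 ATC selection already retrieves the records, so no new data are needed, and that appendix already provides for a SAP revision before lock for conversion factors.

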### **6.10.1. Corticosteroid Dosing Conversion**

To allow for assessments of changes in doses of various corticosteroids, all corticosteroid doses will be standardized to an equivalent prednisone dose. [Appendix 1](#) provides a complete summary of conversion factors for each corticosteroid medication identified during the study, instructions for selecting corticosteroids, and the manual review process. An intramuscular (IM) injection is considered a single dose on the date IM injection is administered. This dose of corticosteroid will be referred to as “prednisone (or equivalent)” throughout this document.

Baseline prednisone (or equivalent) dose will be the total daily dose of all corticosteroids being taken by a patient on the day prior to the date of the first dose of study drug administration (baricitinib). This baseline dose will be used for baseline summaries and for comparisons to later visits. A daily dose of prednisone (or equivalent) will be calculated for each day between baseline and study discontinuation. The corticosteroid dose for a postbaseline visit will be the daily dose of prednisone (or equivalent) at each visit date minus 1.

## **6.11. Efficacy Analyses**

### **6.11.1. General Considerations**

[Table JAIM.6.3](#) includes the description, derivation and definition of missingness of the efficacy and health outcomes measures and endpoints. [Table JAIM.6.4](#) includes the description of the

analysis method, population and primary time point(s) of analysis for efficacy and health outcomes measures. Assessments collected at multiple visits will be analyzed at each visit, in addition to the primary time point. Details of each analysis will follow the general principles described under Analysis Methods in Section [6.4](#).

Table JAIM.6.3. Description and Derivation of Efficacy/Health Outcomes Measures and Endpoints

Measure	Description	Variable	Derivation/Comment	Definition of Missing
SRI-4	SRI-4 is a composite index to measure overall improvement in disease activity (SLEDAI-2K) while ensuring there is no worsening in other organ systems (BILAG and PGA)	SLE Responder Index 4	A decrease in SLEDAI-2K $\geq 4$ (from baseline), and No new BILAG A and no more than 1 new BILAB B organ domain (both compared with baseline), and No worsening in PGA (defined as an increase of 0.3 points [10 mm] from baseline).	Missing, if any component (SLEDAI, BILAG, or PGA) remains missing after each instrument-level imputation rule is applied
SLEDAI-2K	The SLEDAI-2K is a global disease activity instrument that focuses on high-impact disease manifestations across 9 organ domains: constitutional, mucocutaneous, musculoskeletal, vascular, cardiorespiratory, central nervous system, immunologic, renal, and hematologic.	SLEDAI-2K Total Score	Calculated by summing the weighted organ manifestations. For the Renal domain, when the urinary casts, hematuria, and pyuria items are “not done” or “not accessed”, they will be coded as “not present”.	If any item scores or all items are missing (not done or not assessed), but the visit occurred, data for that item can be carried forward if obtained within the previous 36 days of visit.
		Individual Organ Domain Improvement defined by SLEDAI-2K	Among patients with SLEDAI-2K score $>0$ within the organ domain at baseline and able to decrease SLEDAI-2K (from baseline) within each organ domain score, separately.	Missing if any SLEDAI-2K item for that organ domain remains missing after instrument-level imputation rules are applied.
		Individual Organ Domain Worsening defined by SLEDAI-2K	Among patients with at least 1 SLEDAI-2K item = 0 in the organ domain score at baseline and able to increase SLEDAI-2K (from baseline) within each organ domain score, separately.	Missing if any SLEDAI-2K item for that organ domain remains missing after instrument-level imputation rules are applied.
		No worsening from baseline in SLEDAI-2K	No increment from baseline of $>0$ points in SLEDAI-2K.	Missing if any SLEDAI-2K item for that organ domain remains missing after instrument-level imputation rules are applied.
BILAG-2004	BILAG-2004 assesses 97 clinical signs, symptoms and laboratory	BILAG	A, B, C, D, or E score will be used in analyses for each of the 9 individual	Within each organ domain (except renal and hematological), any

Measure	Description	Variable	Derivation/Comment	Definition of Missing
	parameters across nine organ system domains: constitutional, mucocutaneous, neuropsychiatric, musculoskeletal, cardiorespiratory, gastrointestinal, ophthalmic, renal and hematological		organ systems.	
missing data will be assumed to be 'Not present' if there is at least 1 nonmissing item in that organ. If all items in 1 organ domain are completely missing but the visit occurred, then the letter score of that organ from the previous visit will be pulled forward, provided data can be obtained within 36 days of visit; otherwise missing except when the letter score from the last nonmissing visit is E, then E score will be pulled forward.
 
For Renal and Hematological domain, if any item is missing but there is at least 1 nonmissing item in the organ, the missing data will be assumed to be "No". If any vital/lab item with "Yes" but vital and lab value is missing, then vital/lab values can be pulled forward, provided data can be obtained within 36 days of visit; otherwise missing. After the value imputation, if the A/B/C score for the organ domain still cannot be derived, then the letter score of that organ from the previous visit will be pulled forward, provided data can be obtained within 36 days of visit; otherwise missing except when the letter score from the last nonmissing visit is E, then E score will be pulled forward.

		BILAG	Reduction of all baseline BILAG A to	Missing if any of 9 domains at

Measure	Description	Variable	Derivation/Comment	Definition of Missing
		improvement	B/C/D and baseline BILAG B to C/D and no BILAG worsening in other organ systems, where worsening is defined as $\geq 1$ new BILAG A or $\geq 2$ new BILAG B	baseline or at the visit remain missing after instrument-level imputation rules are applied, except when the missing is at the baseline (any one or all domains) and the value at the visit is not A or B, then the other nonmissing organ domains will be used to determine the response status.
		No BILAG worsening	No new BILAG A and no $>1$ new BILAG B disease activity score (both compared with baseline), where worsening is defined as $\geq 1$ new BILAG A or $\geq 2$ new BILAG B, both compared with the baseline. The baseline BILAG A improved to BILAG B at the visit will not be considered as the new BILAG B.	Missing if any of 9 domains at baseline or at the visit remains missing after instrument-level imputation rules are applied except when the baseline (any one or all domains) is BILAG A and the value at the visit is missing, then the other nonmissing organ domains will be used to determine the response status.
		Individual Organ Domain Improvement Defined by BILAG	Among patients with BILAG A or B at baseline and able to reduce the baseline BILAG A to B/C/D and BILAG B to C/D for each organ domain, separately.	Missing if baseline or value remains missing after instrument-level imputation rules are applied.
		Individual Organ Domain Worsening Defined by BILAG	Among patients without BILAG A at baseline, an increment of baseline BILAG B/C/D/E to A or baseline BILAG C/D/E to B for each organ domain, separately.	Missing if baseline or value remains missing after instrument-level imputation rules are applied.
Physician's Global Assessment of Disease Activity	The PGA is the physician's assessment of the patient's overall disease activity due to SLE. It is scored using a visual analog scale	PGA score PGA category	Permitted range of values is from 0 to 100 mm. PGA categories are defined as: None (0) = '0 mm', Mild ( $>0$ and $<1.5$ ) = ' $>0$ to $<50$ mm', Moderate ( $\geq 1.5$ to $\leq 2.5$ )	If the visit occurred, data can be carried forward if obtained within 36 days of visit; otherwise missing.

Measure	Description	Variable	Derivation/Comment	Definition of Missing
(PGA)	where 0 mm indicates no disease activity and 100 mm indicates the most severe disease activity possible. There are benchmarks of 0 (0 mm), 1 (33 mm), 2 (67 mm), and 3 (100 mm) on the line corresponding to no, mild, moderate, and severe SLE disease activity, respectively.		= '≥50 mm to ≤83mm', Severe (>2.5) = '>83mm'.	
		No worsening in PGA	Worsening is defined as an increase of ≥0.3 points (10 mm) from baseline. Therefore, no worsening is defined as any decrease, no change, or <0.3 points (10 mm) increase from baseline.	Missing if baseline or value remains missing after instrument-level imputation rules are applied.
		PGA ≤1	PGA ≤33 mm	Missing if value remains missing at the visit after instrument-level imputation rules are applied.
BICLA	BICLA is a composite index to measure overall improvement in disease activity (BILAG) while ensuring there is no worsening in other organ systems (SLEDAI-2K and PGA)	BICLA	
 
Reduction of all baseline BILAG A to B/C/D and baseline BILAG B to C/D and no BILAG worsening in other organ systems, where worsening is defined as ≥1 new BILAG A or ≥2 new BILAG B
 
No worsening from baseline in SLEDAI-2K, where worsening is defined as an increase from baseline of >0 points in SLEDAI-2K
 
No worsening from baseline in participants' lupus disease activity, where worsening is defined by an increase ≥0.30 points on a 3-point PGA visual analogue scale (VAS).
 
	Missing if any component (BILAG, SLEDAI or PGA) remains missing after each instrument level imputation rule is applied.
Cutaneous Lupus Erythematosus Disease Area and Severity Index (CLASI)	The CLASI is a validated instrument to assess cutaneous manifestations of SLE consisting of 2 scores: 
 
Activity
 
Damage
 
	Total Activity Score	Calculated within tablet system with edit checks; no additional derivation.	Within tablet system: if any item scores, but not all, are missing then impute a score of 0 for the missing item(s). For completely missing questionnaires, data can be carried forward if obtained within 36 days of visit; otherwise missing.

Measure	Description	Variable	Derivation/Comment	Definition of Missing
		Total Damage Score	Calculated within tablet system with edit checks; no additional derivation.	Within tablet system: if any item scores, but not all, are missing then impute a score of 0 for the missing item(s). For completely missing questionnaires, data can be carried forward if obtained within 36 days of visit; otherwise missing.
Lupus Low Disease Activity State (LLDAS)	The LLDAS is a composite measure designed to identify patients achieving a state of low disease activity.	LLDAS	
 
SLEDAI-2K <math>\leq 4</math> with no activity in SLEDAI-2K major organ systems (CNS, Vascular, Renal, cardiorespiratory, and constitutional), where “no activity” is defined as all items of SLEDAI-2K within these major organ systems = 0.
 
No new features of Lupus disease activity in SLEDAI-2K compared to previous occurred visit, where the “new feature” is defined as any of SLEDAI-2K 24 items changed from 0 to <math>>0</math>.
 
PGA <math>\leq 1</math>
 
Current prednisone or equivalent dose <math>\leq 7.5</math> mg/day
 
	Missing if any component remains missing after each instrument-level imputation rule is applied.
SFI flare	The SFI uses the SLEDAI score, disease activity scenarios, treatment changes, and PGA to define mild/moderate and severe flares.	SFI flare	Not derived; used as entered.	The absence of a flare record, or ‘Not Applicable’, both are indicative of no occurrence of flare.
		Annualized flare rate	Calculated as the number of SFI flares divided by the flare exposure time in days multiplied by 365.25.	No minimum data requirement.
Tender/Swollen Joint Count (28 Joints)	28 joints are assessed as tender only, swollen only, tender and swollen, not evaluable.	Tender Joint Count 28/ Swollen Joint Count 28	The number of tender and swollen joints will be calculated by summing all joints respectively.	For patients who have an incomplete set of joints evaluated, the joint count will be adjusted to a 28-joint count for tenderness and a 28-joint count

Measure	Description	Variable	Derivation/Comment	Definition of Missing
				for swelling by dividing the number of affected joints by the number of evaluated joints and multiplying by 28.
Systemic Lupus International Collaborating Clinics/American College of Rheumatology Damage Index (SLICC/ACR)	SLICC/ACR Damage Index assesses damage to 12 organ systems regardless of its cause.	SLICC/ACR Damage Index Score	Calculated as the sum of all available entries with a maximum score of 47.	“Missing” item is coded as 0.
Worst Pain NRS	This Worst Pain NRS is a single-item patient-administered 11-point horizontal scale anchored at 0 (no pain) and 10 (pain as bad as you can imagine)	Worst Pain NRS score	Permitted range of values is from 0 to 10.	Single item, missing if missing.
FACIT-Fatigue	The FACIT-Fatigue scale (Cella and Webster 1997) is a 13-item symptom-specific questionnaire that assesses self-reported severity of fatigue and its impact upon daily activities and functioning.	FACIT-Fatigue total score	The FACIT-F uses 0 (“not at all”) to 4 (“very much”) numeric rating scales to assess fatigue and its impact in the past 7 days. Scores range from 0 to 52 with higher scores indicating less fatigue. The FACIT-Fatigue Scoring Guidelines (Version 4) will be used to calculate the Total Score. Reversals are needed for all items except An5 and An7, as described in scoring manual. http://www.ser.es/wp-content/uploads/2015/03/FACIT-F_INDICE.pdf .	Missing items are acceptable as long as more than 50% of the items are answered (ie, a minimum of 7 out of 13 items), the sum of available items will be multiplied by 13 then divided by the number of items answered to obtain the total score. If less than 7 items are answered, the FACIT-Fatigue total score will be set to missing.
Steroid sparing	This measures the change in corticosteroid dose through week 156	Corticosteroid Dose	See Section 6.10.1 for detailed derivations.	No minimum data requirement.
Worst Joint Pain NRS	This Worst Joint Pain NRS is a single-item, patient-administered 11-point horizontal scale anchored at 0	Worst Joint Pain NRS Score	Permitted range of values is from 0 to 10.	Single item, missing if missing.

Measure	Description	Variable	Derivation/Comment	Definition of Missing
	(no joint pain) and 10 (joint pain as bad as you can imagine)			
Worst Fatigue NRS	This Worst Fatigue NRS is a patient-administered 11-point horizontal scale anchored at 0 (no fatigue) and 10 (fatigue as bad as you can imagine)	Worst Fatigue NRS Score	Permitted range of values is from 0 to 10.	Single item, missing if missing.
Patient Global Impression of Severity	The Patient’s Global Impression of Severity is a single-item question asking the patient how they would rate their overall lupus symptoms over the last 24 hours.	Patient Global Impression of Severity Score	Possible values are: (0) No symptoms, (1) Very mild, (2) Mild (3) Moderate (4) Severe	Single item, missing if missing.
SF-36 v2 Acute	
The SF-36 Version 2 acute (1-week recall) is a 36-item, patient-completed measure designed to be a short, multipurpose assessment of health (The SF Community – SF-36 Health Survey Update). The summary scores range from 0 to 100, with higher scores indicating better levels of function and/or better health.
 
Items are answered on Likert scales of varying lengths. The SF-36 comprises 8 domain scores and 2 overarching component scores. SF-36 domain scores are: (1) Physical functioning, (2) Role-physical, (3) Role-emotional, (4) bodily pain, (5) vitality, (6) social functioning, (7) mental health and (8) general health.
 
The component scores are: (1) the
	SF-36 Domain scores and SF-36 Component Scores	
Per copyright owner, the Quality Metric Health Outcomes™ Scoring Software will be used to derive SF-36 domain and component scores.
 
SF-36V2 Normed-Based Scoring will be used for the domain and component scores and includes 2 steps: 1/ z-score standardization of SF-36v2 scales; and 2/ norm-based transformation of the SF-36v2 z scores. 2009 norms will be used. (Maruish 2011).
	Missing data handling offered by SF-36 software will be used. Maximum Data Recovery will be selected for Missing Score Estimator in the software.

Measure	Description	Variable	Derivation/Comment	Definition of Missing
	Physical Component Summary (PCS) and (2) Mental Component Summary (MCS).			
EQ-5D-5L	
The European Quality of Life–5 Dimensions–5 Level (EQ-5D-5L) is a standardized measure of health status used to provide a simple, generic measure of health for clinical and economic appraisal. The EQ-5D-5L consists of 2 components: a descriptive system of the respondent’s health and a rating of his/her current health state using a 0- to 100-mm VAS.
 
The descriptive system comprises the following 5 dimensions:
 
 
Item 1: mobility
 
Item 2: self-care
 
Item 3: usual activities
 
Item 4: pain/discomfort
 
Item 5: anxiety/depression
 
 
The respondent is asked to indicate his/her health state by ticking (or placing a cross) in the box associated with the most appropriate statement in each of the 5 dimensions.
 
It should be noted that the numerals 1 to 5 have no arithmetic properties and should not be used as an ordinal score. The VAS records the respondent’s self-rated health on a vertical VAS where the endpoints are
	EQ-5D-5L Items	
Five health profile dimensions, each dimension has 5 levels:
 
 
1 = no problems
 
2 = slight problems
 
3 = moderate problems
 
4 = severe problems
 
5 = extreme problems
 
 
It should be noted that the numerals 1 to 5 have no arithmetic properties and should not be used as a primary score.
	Each dimension is a single item, missing if missing. Note: a score of 9 is missing.
		EQ-5D-5L UK/US Population-based index score	
Uses the concatenation of the value of each EQ-5D-5L dimension score in the order: Item 1, Item 2, Item3; Item 4; Item 5.
 
Derive EQ-5D-5L UK/US Population-based index score according to the link by using the UK/US algorithm (Szende et al. 2006) to produce a patient-level index score between -0.59 and 1.0 (continuous variable):
 
https://euroqol.org/eq-5d-instruments/eq-5d-5l-about/valuation-standard-value-sets/crosswalk-index-value-calculator/.
	If any of the items is missing or equal to 9, the index score is missing
		EQ-5D VAS	
Single item. Range from 0 = “worst imaginable health state” to 100 = “best imaginable health state”.
 
Note: higher value indicates better health state.
	Single item, missing if missing

Measure	Description	Variable	Derivation/Comment	Definition of Missing
	
labeled “best imaginable health state” and “worst imaginable health state.” This information can be used as a quantitative measure of health outcome.
 
The EQ 5D 5L health states, defined by the EQ 5D 5L descriptive system, may be converted into a single summary index by applying a formula that essentially attaches values (also called weights) to each of the levels in each dimension (Herdman et al. 2011; EuroQol Group 2015 [WWW]).
			
WPAI-Lupus	
The Work Productivity and Activity Impairment – Lupus (WPAI-Lupus) is a patient-reported instrument developed to measure the impact on work productivity and regular activities attributable to SLE. It contains 6 items that measure: 1) employment status, 2) hours missed from work due to the specific health problem, 3) hours missed from work for other reasons, 4) hours actually worked, 5) degree health affected productivity while working, and 6) degree health. Scores are calculated as impairment percentages (Reilly et al. 1993), with higher scores indicating greater productivity impairment.
	Employment Status	Yes/No	Missing if answer is missing
		Absenteeism Score (%)	$\frac{Q2}{(Q2 + Q4)} \times 100$	Missing if Q2 or Q4 are missing. Also missing if Employment Status is No.
		Presenteeism Score (%)	$\frac{Q5}{10} \times 100$	Missing if Q5 is missing. Also missing if Employment Status is No.
		Work productivity Loss Score (%)	$\left[ \frac{Q2}{Q2 + Q4} + \left( 1 - \frac{Q2}{Q2 + Q4} \right) \frac{Q5}{10} \right] \times 100$	Missing if Q2, Q4 or Q5 is missing. Also missing if Employment Status is No.
		Activity Impairment Score (%)	$\frac{Q6}{10} \times 100$	Missing if Q6 is missing. May still be present and nonmissing if patient is unemployed.

Abbreviations: BICLA = British Isles Lupus Assessment Group-based Composite Lupus Assessment; BILAG = British Isles Lupus Activity Group; CNS = Central Nervous System; FACIT = Functional Assessment of Chronic Illness Therapy; MCS= Mental Component Score; NRS = Numeric Rating Scale; PGA = Physician's Global Assessment; PCS= Physical Component Summary; SRI-4 = Systemic Lupus Erythematosus (SLE) Responder Index; SLEDAI-2K = Systemic Lupus Erythematosus Disease Activity Index 2000; SFI = SLEDAI Flare Index; SF-36 = Short Form 36; V = visit; VAS = Visual Analog Scale.

